9.2 Ethical Conduct of the Study

The study will be performed in accordance with the ethical principles that have their origin in the Declaration of Helsinki, ICH GCP, the protocol, and all applicable regulations.

9.3 Patient Information and Consent

Written informed consent in compliance with regulatory authority regulations shall be obtained from each patient before entering the study or performing any unusual or nonroutine procedure that involves risk to the patient. An informed consent template may be provided by the sponsor to investigative sites. If any institution-specific modifications to study-related procedures are proposed or made by the site, the consent should be reviewed by the sponsor or its designee or both before IRB/IEC submission. Once reviewed, the consent will be submitted by the investigator to his or her IRB/IEC for review and approval before the start of the study. If the ICF is revised during the course of the study, all active participating patients must sign the revised form.

Before recruitment and enrollment, each prospective patient or his or her legal guardian will be given a full explanation of the study and be allowed to read the approved ICF. Once the investigator is assured that the patient/legal guardian understands the implications of participating in the study, the patient/legal guardian will be asked to give consent to participate in the study by signing the ICF. The investigator shall retain the signed original ICF(s) and give a copy of the signed original form to the patient or legal guardian.

10 Investigator's Obligations

The following administrative items are meant to guide the investigator in the conduct of the study but may be patient to change based on industry and government standard operating procedures, working practice documents, or guidelines. Changes will be reported to the IRB/IEC but will not result in protocol amendments.

10.1 Confidentiality

All laboratory specimens, evaluation forms, reports, and other records will be identified in a manner designed to maintain patient confidentiality. All records will be kept in a secure storage area with limited access. Clinical information will not be released without the written permission of the patient (or the patient's legal guardian), except as necessary for monitoring and auditing by the sponsor, its designee, the US Food and Drug Administration (FDA), or the IRB/IEC.

The investigator and all employees and coworkers involved with this study may not disclose or use for any purpose other than performance of the study any data, record, or other unpublished, confidential information disclosed to those individuals for the purpose of the study. Prior written agreement from the sponsor or its designee must be obtained for the disclosure of any said confidential information to other parties.

10.2 Financial Disclosure and Obligations

Investigators are required to provide financial disclosure information to allow the sponsor to submit the complete and accurate certification or disclosure statements required under 21 Code of Federal Regulations (CFR) 54. In addition, the investigator must provide to the sponsor a commitment to promptly update this information if any relevant changes occur during the course of the investigation and for 1 year following the completion of the study.

Neither the sponsor nor [REDACTED] is financially responsible for further testing or treatment of any medical condition that may be detected during the screening process. In addition, in the absence of specific arrangements, neither the sponsor nor [REDACTED] is financially responsible for further treatment of the patient's disease.

10.3 Investigator Documentation

Prior to beginning the study, the investigator will be asked to comply with ICH E6 (R2) 8.2 and Title 21 of the CFR by providing the following essential documents, including but not limited to:

- IRB/IEC approval
- Original investigator-signed investigator agreement page of the protocol

- Form FDA 1572, fully executed, and all updates on a new fully executed Form FDA 1572
- Curriculum vitae (CV) for the investigator and each subinvestigator listed on Form FDA 1572
- Medical License (ML) for the investigator and each applicable subinvestigator listed on Form FDA 1572
- Financial disclosure information to allow the sponsor to submit complete and accurate certification or disclosure statements required under 21 CFR 54. In addition, the investigators must provide to the sponsor a commitment to promptly update this information if any relevant changes occur during the course of the investigation and for 1 year after the completion of the study.
- IRB/IEC-approved informed consent, samples of site advertisements for recruitment for this study, and any other written information regarding this study that is to be provided to the patient or legal guardian, and
- Laboratory certifications and normal ranges for any local laboratories used by the site, in accordance with 42 CFR 493

10.4 Study Conduct

The investigator agrees that the study will be conducted according to the principles of ICH E6 (R2). The investigator will conduct all aspects of this study in accordance with all national, state, and local laws or regulations. Study information from this protocol will be posted on publicly available clinical study registers before enrollment of patients begins.

10.5 Adherence to Protocol

The investigator agrees to conduct the study as outlined in this protocol in accordance with ICH E6 (R2) and all applicable guidelines and regulations.

10.6 Adverse Events and Study Report Requirements

By participating in this study, the investigator agrees to submit reports of SAEs to the sponsor and/or IRB/IEC according to the timeline and method outlined in the protocol. In addition, the investigator agrees to submit annual reports to the study site IRB/IEC as appropriate.

10.7 Investigator's Final Report

Upon completion of the study, the investigator, where applicable, should inform the institution; the investigator/institution should provide the IRB/IEC with a summary of the study's outcome and the sponsor and regulatory authority(ies) with any reports required.

10.8 Records Retention

Essential documents should be retained until at least two years after the last approval of a marketing application in an ICH region and until there are no pending or contemplated marketing applications in an ICH region or at least two years have elapsed since the formal discontinuation of clinical development of the study treatment. These documents should be retained for a longer period, however, if required by the applicable regulatory requirements or by an agreement with the sponsor. It is the responsibility of the sponsor to inform the investigator/institution as to when these documents no longer need to be retained.

10.9 Publications

After completion of the study, the data may be considered for reporting at a scientific meeting or for publication in a scientific journal. In these cases, the sponsor will be responsible for these activities and will work with the investigators to determine how the manuscript is written and edited, the number and order of authors, the publication to which it will be submitted, and other related issues. The sponsor has final approval authority over all such issues.

Data are the property of the sponsor and cannot be published without prior authorization from the sponsor, but data and publication thereof will not be unduly withheld.

11 Study Management

The administrative structure will include a DSMB and EAC.

11.1 Monitoring

11.1.1 Independent Data Safety Monitoring Board

During the study, an independent DSMB will periodically review accumulating unblinded safety data and SAE/AE in real time. The detailed description is provided in [Section 6.6](#).

11.1.2 Monitoring of the Study

The clinical monitor, as a representative of the sponsor, has the obligation to follow the study closely. In doing so, the monitor will visit the investigator and study site at periodic intervals, in addition to maintaining necessary telephone and letter contact. The monitor will maintain current personal knowledge of the study through observation, review of study records and source documentation, and discussion of the conduct of the study with the investigator and personnel.

All aspects of the study will be carefully monitored, by the sponsor or its designee, for compliance with applicable government regulation with respect to current GCP and current standard operating procedures.

11.1.3 Inspection of Records

Investigators and institutions involved in the study will permit study-related monitoring, audits, IRB/IEC review, and regulatory inspections by providing direct access to all study records. In the event of an audit, the investigator agrees to allow the sponsor, representatives of the sponsor, or a regulatory agency access to all study records.

The investigator should promptly notify the sponsor and [REDACTED] of any audits scheduled by any regulatory authorities and promptly forward copies of any audit reports received to the sponsor.

11.2 Management of Protocol Amendments and Deviations

11.2.1 Modification of the Protocol

Any changes in this research activity, except those necessary to remove an apparent, immediate hazard to the patient, must be reviewed and approved by the sponsor or its designee. Amendments to the protocol must be submitted in writing to the investigator's IRB/IEC for approval before patients can be enrolled into an amended protocol.

11.2.2 Protocol Deviations

The investigator or designee must document and explain in the patient's source documentation any deviation from the approved protocol. The investigator may implement a deviation from,

or a change of, the protocol to eliminate an immediate hazard to study patients without prior IRB/IEC approval. As soon as possible after such an occurrence, the implemented deviation or change, the reasons for it, and any proposed protocol amendments should be submitted to the IRB/IEC for review and approval, to the sponsor for agreement, and to the regulatory authorities, if required.

A deviation from the protocol is an unintended or unanticipated departure from the procedures or processes approved by the sponsor and the IRB/IEC and agreed to by the investigator. A significant deviation occurs when there is nonadherence to the protocol by the patient or investigator that results in a significant, additional risk to the patient. Significant deviations can include nonadherence to inclusion or exclusion criteria, or nonadherence to FDA regulations or ICH GCP guidelines, and will lead to the patient being withdrawn from the study ([Section 4.2](#)).

Protocol deviations will be documented by the clinical monitor throughout the course of monitoring visits. Principal investigators will be notified in writing by the monitor of deviations. The IRB/IEC should be notified of all protocol deviations in a timely manner.

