4.2 Withdrawal of Patients from Study Treatment and/or the Study

The duration of the study is defined for each patient as the date signed written informed consent is provided through the last safety follow-up visit at Visit 8. If a patient discontinues treatment, they will be encouraged to remain in the study and continue study visits and procedures for the full course of the study without receiving study treatment. Patients who withdraw from the

study before the Visit 7/ET visit and are not willing to continue study visits and procedures for the full course of the study will be asked, to undergo an ET visit that will include all evaluations that were intended to be performed at the final visit.

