4.2.3 Replacements

Patients who withdraw, are withdrawn by the investigator, or are lost to follow-up after randomization will not be replaced.

5 Study Treatments

The study treatment will be oral capsules containing 75 mg and 100 mg of pridopidine and matching placebo capsules (as the control treatment product) identical in appearance.

Pridopidine capsules contain the active ingredient pridopidine (75 mg or 100 mg) and inactive excipients. The excipients are [REDACTED].

The investigational product will be produced and packed in 60 count bottles provided by [REDACTED]

The secondary packaging and labeling of study treatment will be performed by [REDACTED]. All packaging and labeling operations for study treatment will be performed according to Good Manufacturing Practice for Medicinal Products and the relevant regulatory requirements.

Bottles containing the investigational product or placebo capsules will be packed in kits. Each medication kit will contain two distinct labeled bottles in accordance with the associated treatment arm. Both outer pack and bottles will be labeled with a unique pack number.

Four types of kit will be prepared for use in this study:

- Kit type 1: One bottle of 75 mg pridopidine and one bottle of placebo
- Kit type 2: One bottle of 100 mg pridopidine and one bottle of placebo
- Kit type 3: Two bottles of 75 mg pridopidine
- Kit type 4: Two bottles of placebo

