7.7 Analysis Sets

The following analysis sets will be used in the statistical analyses.

Intent-to-Treat (ITT) Set: The ITT set will include all randomized patients. The patients will be grouped as randomized. Retrieved drop-out data (data captured from the drop-outs after the end-of-study visit when the patient is free of study treatment) will not be included in the ITT set. The ITT set will be used for the sensitivity analysis of the primary endpoint.

Modified Intent-to-Treat (mITT) Set: The mITT set will include all randomized patients who receive a dose of study treatment and have efficacy assessments both at Baseline (Visit 2) and at least one post-randomization time point. The patients will be grouped as randomized. Retrieved drop-out data (data captured from the drop-outs after the end-of-study visit when the patient is free of study treatment) will not be included in the determination of the mITT set. The mITT set will be used for the efficacy analysis.

Completer Set: The completer set is a subset of the mITT set and includes the subsets of patients with efficacy data at Visit 7/ET.

The patients will be grouped as randomized. The completer set will be used for the sensitivity analysis of the primary endpoint.

Safety Set: The safety set will consist of all patients receiving at least one dose of study treatment. The patients will be grouped according to the treatment regimen actually received at Visit 3. The safety set will be used for the safety analyses.

PK Set: The PK set will consist of all patients in the safety set with at least one pridopidine concentration sample result reported. The PK set will be used for the PK analyses.

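### Protocol Section 11.2.2 makes withdrawal from the study mandatory after a significant deviation. Section 4.2, which it cites, has no such rule and favours keeping patients in follow-up.

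*Protocol*

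**What the plan says.** Protocol Section 11.2.2 defines a significant deviation as "nonadherence to the protocol by the patient or investigator that results in a significant, additional risk to the patient". It then gives examples: "Significant deviations can include nonadherence to inclusion or exclusion criteria", and failure to follow FDA regulations "or ICH GCP guidelines, and will lead to the patient being withdrawn from the study". The cross-reference is to Section 4.2.

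Section 4.2 deals with leaving treatment and leaving the study. Its retention sentence reads "If a patient discontinues treatment, they will be encouraged to remain in the study and continue study visits", for the full course and without study treatment. Patients who leave before Visit 7 and are not willing to continue "will be asked, to undergo an ET visit that will include all evaluations that were intended to be performed at the final visit". Neither 4.2 nor 4.2.1 names a protocol deviation as a reason for withdrawal.

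Under Section 4.2.3, patients who withdraw, those whom the investigator withdraws and those who "are lost to follow-up after randomization will not be replaced".

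On analysis, Section 7.7 states: "The ITT set will include all randomized patients. The patients will be grouped as randomized".

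**The concern.** The rule in 11.2.2 is mandatory, it concerns the study and not only treatment, and nonadherence by the investigator can trigger it. The section cited as its basis points the other way. Take a patient found after randomisation to have missed an exclusion criterion in a way that adds significant risk, and whose treatment is stopped. Section 4.2 encourages that patient to keep attending, while 11.2.2 takes the patient out of the study. A site cannot act on both.

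Three things are at stake. First, outcome data go missing because of an event after randomisation, when they could have been collected. Such an event may be related to treatment or symptoms, although the documents do not show that it would be. Second, the retrieved drop-out sensitivity analysis depends on visits made after treatment stops, and the rule prevents those visits. If treatment would otherwise have continued, on-treatment visits are lost as well. Third, the rule applies by definition to patients at added risk, and it ends their scheduled ECG, laboratory and adverse-event visits early.

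**Working it through.** **The passages side by side**

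| Protocol section | Trigger | Consequence | Force |
|---|---|---|---|
| 11.2.2 | Significant deviation by patient or investigator | Withdrawn from the study | Mandatory |
| 4.2 | Treatment discontinued | Stay for the full course, off treatment | Encouraged |
| 4.2.1 | Illness, adverse event, non-cooperation, health or well-being | Investigator may withdraw the patient | Discretionary |
| 5.8.1 | Patient unblinded | Treatment stops, patient stays until the final visit | Encouraged |
| 7.9.1 | Patient discontinues | Scheduled efficacy assessments still sought | All efforts |

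The last four rows either favour retention or leave withdrawal to judgement. Section 11.2.2 stands alone among them in requiring study withdrawal, and it relies on a section that does not contain the rule.

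**The plan's own sample size**

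Inputs from Protocol Section 7.6: difference 8.5 points, SD 13, two-sided alpha 0.05, power 80%, drop-out 15%.

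- Two-sample t-test, noncentrality = 8.5 / (13 × √(2/n)). The smallest n per arm with at least 80% power is 38, where power is 80.3%.
- 38 × 3 = 114, and 114 / 0.85 = 134.1, rounded up to 135, or 45 per arm.

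The stated figures of 38, 114 and 135 reproduce.

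**What extra withdrawals could do to power**

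The documents give no rate of significant deviations. As an assumption, let a fraction x of patients lose Visit 7 data through this rule, wholly on top of the 15%. Patients left per arm = 45 × (1 − 0.15 − x).

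| x (assumed) | Patients of 135 | Left per arm | t-test power |
|---|---|---|---|
| 0% | 0 | 38.3 | 80.6% |
| 2% | 2.7 | 37.4 | 79.6% |
| 5% | 6.75 | 36.0 | 78.1% |
| 10% | 13.5 | 33.8 | 75.4% |

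If these withdrawals are already part of the 15%, the first row applies whatever x is. Section 7.6 does not break the drop-out figure down, so either reading is possible. The table also treats each withdrawn patient as contributing nothing, although the repeated-measures model would use that patient's earlier visits. It is an illustration, and the contradiction does not depend on it.

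**What the later SAP changes**

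SAP Section 2 says that the SAP prevails over the protocol where they differ. SAP Section 5.1 defines EE1 and EE2 by being on treatment at Visit 3 or Visit 5, with at least 80% of dosing or compliance, and it has no ITT set. Off-treatment follow-up would not qualify a patient for EE2. SAP Section 13 puts deviations in listings only. The SAP does not address the conflict about conduct.

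**The case against.** The strongest reply is that the two rules differ in scope. Section 4.2 speaks of patients who stop treatment and only encourages them to stay; it does not say who may be withdrawn from the study. Section 4.2.1 allows withdrawal for any reason concerning the patient's health or well-being, and its stopping rules are introduced as some reasons among others. Since 11.2.2 defines significant deviations by added risk, most would fall under that discretion anyway. This stands in part: the clash is between a mandatory rule and a retention policy, not between two rules of identical scope. It does not remove the clash, because a discretion and an obligation are different instructions to a site.

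Several stronger readings are tempting, and the documents do not support them.

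- A reader might infer that any GCP breach by a site forces withdrawal. The added-risk condition in the definition limits the rule.
- A reader might infer that observation ends at one early-termination visit. Section 3.1.3 places a safety visit two weeks after Visit 7/ET, Section 4.2.2 encourages the final evaluations, and Sections 6.5.1.1 and 6.5.1.10 follow adverse events until they resolve or are stable. One qualification is that Section 4.2 words the early-termination visit for patients unwilling to continue, not for those removed by rule.
- A reader might infer that the as-randomised analysis is defeated. Section 11.2.2 drops no one from an analysis set. The patient stays in ITT, and in mITT if dosed and with efficacy assessments at baseline and at least once after randomisation. Section 7.9.1 provides multiple imputation under two missing-data assumptions. Retrieved drop-out data are excluded from the main sets and enter only a sensitivity analysis.
- A reader might take starting a prohibited medicine as a named trigger. The examples in 11.2.2 are eligibility and FDA or GCP nonadherence.

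**Conclusion.** The concern holds as an internal contradiction with a real but unquantified cost. Section 11.2.2 requires study withdrawal, and its cited basis contains no such rule and leans the other way. If sites follow it, scheduled visits are lost for unreplaced patients at added risk, the retrieved drop-out sensitivity analysis is weakened, and safety follow-up is shorter than it need be.

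The number of patients is unknown. Power falls from 80.6% to between 79.6% and 75.4% only if one assumes 2% to 10% extra loss on top of the 15%. If the loss is inside the 15%, it does not fall at all. A claim that the trial would drop below 38 per arm therefore rests on that assumption and not on the documents. Possible bias from removal after randomisation matters more than power. Under the SAP as now in force the effect on the planned analysis is small, because the EE sets are on-treatment sets and the trial was stopped before 30 patients were enrolled (SAP Section 9.3). The wording should still be corrected, since the SAP leaves it untouched.

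**What to change.** Reconcile Section 11.2.2 with Sections 4.2 and 4.2.1 so that a deviation alone does not end study follow-up. Any decision on study treatment should be handled separately under the rules that already exist, and the patient encouraged to continue scheduled visits as Section 4.2 provides.

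Leave the other withdrawal provisions as they are: the investigator's right in 4.2.1, the safety board's authority in 6.6 and withdrawal for pregnancy in 6.7. Wording that allowed withdrawal only when consent is withdrawn would contradict all three.

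For the trial as terminated, SAP Section 10 already tabulates the primary reason for discontinuation. Use that table to identify any patient withdrawn because of a deviation.

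The cost is one sentence of protocol text, the remaining scheduled visits for a few patients, and one entry in the disposition table.

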11.3 Study Termination

Although Prilenia Therapeutics has every intention of completing the study, Prilenia Therapeutics reserves the right to discontinue the study at any time for clinical or administrative reasons.

The end of the study will be defined as the final date on which data were (or are expected to be) collected.

